**Table 5.4.2-2: Assessment of Best Overall Response**

[figure not shown]
Best Overall Response	Criteria
Complete Response (CR)	CR observed in consecutive assessments ≥ 4 weeks apart per RANO
Partial Response (PR)	PR observed in consecutive assessments ≥ 4 weeks apart per RANO
Stable Disease (SD) a	SD observed and does not qualify for CR or PR or Suspected PD followed with histologic results not confirming PD, and no CR, PR or SD observed

**Table 5.4.2-2: Assessment of Best Overall Response**

[figure not shown]
Best Overall Response	Criteria
Not Evaluable (NE)	Insufficient data to determine disease progression or response
Progressive Disease (PD)	No CR, PR, or SD prior to PD

[figure not shown]
a To qualify for SD there must be a minimum on-treatment period of 10 weeks.

The minimum duration between baseline post-operative scan and first on-study scan in order to determine BOR of SD is 4 weeks after completion of RT. If the minimum time is not met when SD is otherwise the best time point response, the subject's best response will depend on the subsequent assessments. For example, a subject who has SD at a time point < 4 weeks post-RT and PD at a second assessment will have a best response of PD.

### **5.6.1 Tumor Samples**

[REDACTED] Tumor tissue (block or slides) must be available for submission prior to randomization. If a block is not available, a minimum of 20 unstained slides of good quality is required. In situations where on-treatment biopsies or surgeries are performed, tumor sample should be sent for central pathology reading.

#### **5.6.1.1 Tumor Sample Collection Details**

Collection of tumor tissue at diagnostic surgery is required for study eligibility. Additional biopsies obtained at any time, eg, if progression is suspected, should also be submitted.

Biopsy samples from neurosurgical resections should be fixed in 10% Neutral-buffered formalin for 24 – 48 hours prior to paraffin embedding. Tumor tissue samples should not be shipped in formalin as the temperature and length of fixation cannot be controlled during shipping.

[REDACTED] 2 paraffin blocks are requested (1 minimum). If only slides are available, they should be unstained, have a recommended tissue section thickness of 4 microns and be positively charged. Slides must be shipped refrigerated at 2-8° C.

[figure not shown]
An assessment of tissue quality by a pathologist is strongly encouraged at the time of the procedure.

[figure not shown]
Sample shipments should include a completed requisition form containing collection date, collection method, primary/met, site, fixation conditions, and a copy of the pathology report, if available.

[figure not shown]
Detailed instructions of the obtaining, processing, labeling, handling, storage, and shipment of specimens will be provided in a separate Procedure Manual at the time of study initiation.

**5.6.1.2 MGMT Status**

Randomization to this study is limited to subjects with established MGMT-methylated or indeterminate status. Testing will be performed using a centralized RT-PCR assay through study CA209498.

## 5.8 Other Assessments

### 5.8.1 Results of Central Pathology Reading

In situations where on-treatment biopsies or surgeries are performed, tumor sample should be sent for central pathology reading. Instructions for shipping biopsy samples/slides can be found in the lab manual. Investigators will receive central pathology results.

### 5.8.3 Results of Central Radiology Assessments

The clinical management of subjects during the study protocol and PFS will be based upon local radiologic tumor measurements and the investigator-assessed RANO response criteria described in [Section 1.2](#). Radiologic imaging from this study will be also be transmitted to a centralized imaging core lab until study unblinding for storage and for analysis by blinded independent central review. The site will be informed of quality issues or need for repeat scanning via queries from the core lab.

## 6 ADVERSE EVENTS

An *Adverse Event (AE)* is defined as any new untoward medical occurrence or worsening of a preexisting medical condition in a clinical investigation subject administered study drug and that does not necessarily have a causal relationship with this treatment. An AE can therefore be any unfavorable and unintended sign (such as an abnormal laboratory finding), symptom, or disease

temporally associated with the use of study drug, whether or not considered related to the study drug.

The definition of immune-mediated AEs can be found in [Section 0](#).

The causal relationship to study drug is determined by a physician and should be used to assess all adverse events (AE). The causal relationship can be one of the following:

Related: There is a reasonable causal relationship between study treatment administration (including SOC) and the AE.

Not related: There is not a reasonable causal relationship between study treatment administration and the AE.

The term "reasonable causal relationship" means there is evidence to suggest a causal relationship. In this study the relationship may be assessed to any component of the study treatment: radiation therapy, TMZ, and/or nivolumab/placebo.

Adverse events can be spontaneously reported or elicited during open-ended questioning, examination, or evaluation of a subject. (In order to prevent reporting bias, subjects should not be questioned regarding the specific occurrence of one or more AEs.)

BMS will be reporting adverse events to regulatory authorities and ethics committees according to local applicable laws including European Directive 2001/20/EC and FDA Code of Federal Regulations 21 CFR Parts 312 and 320.

## 6.1 Serious Adverse Events

A *Serious Adverse Event (SAE)* is any untoward medical occurrence that at any dose:

- results in death
- is life-threatening (defined as an event in which the subject was at risk of death at the time of the event; it does not refer to an event which hypothetically might have caused death if it were more severe)
- requires inpatient hospitalization or causes prolongation of existing hospitalization (see **NOTE** below)
- results in persistent or significant disability/incapacity
- is a congenital anomaly/birth defect
- is an important medical event (defined as a medical event(s) that may not be immediately life-threatening or result in death or hospitalization but, based upon appropriate medical and scientific judgment, may jeopardize the subject or may require intervention [eg, medical, surgical] to prevent one of the other serious outcomes listed in the definition above.) Examples of such events include, but are not limited to, intensive treatment in an emergency room or at home for allergic bronchospasm; blood dyscrasias or convulsions that do not result in hospitalization.) Potential drug induced liver injury (DILI) is also considered an important medical event. (See [Section 6.6](#) for the definition of potential DILI)

Suspected transmission of an infectious agent (eg, pathogenic or nonpathogenic) via the study drug is an SAE.

Although pregnancy, overdose, cancer, and potential drug induced liver injury (DILI) are not always serious by regulatory definition, these events must be handled as SAEs. (See Section 6.1.1 for reporting pregnancies).

Any component of a study endpoint that is considered related to study therapy (eg, death is an endpoint, if death occurred due to anaphylaxis, anaphylaxis must be reported) should be reported as SAE. (See Section 6.1.1 for reporting details).

**NOTE:**

The following hospitalizations are not considered SAEs in BMS clinical studies:

- a visit to the emergency room or other hospital department < 24 hours, that does not result in admission (unless considered an important medical or life-threatening event)
- elective surgery, planned prior to signing consent
- admissions as per protocol for a planned medical/surgical procedure
- routine health assessment requiring admission for baseline/trending of health status (eg, routine colonoscopy)
- medical/surgical admission other than to remedy ill health and planned prior to entry into the study. Appropriate documentation is required in these cases
- admission encountered for another life circumstance that carries no bearing on health status and requires no medical/surgical intervention (eg, lack of housing, economic inadequacy, caregiver respite, family circumstances, administrative reason)
- admission for administration of anticancer therapy in the absence of any other SAEs

**6.1.1 Serious Adverse Event Collection and Reporting**

Sections 5.6.1 and 5.6.2 in the Investigator Brochure (IB) represent the Reference Safety Information to determine expectedness of serious adverse events for expedited reporting. Following the subject's written consent to participate in the study, all SAEs, whether related or not related to study drug, must be collected, including those thought to be associated with protocol-specified procedures. All SAEs, and all AEs (SAEs and non-serious AEs) associated with confirmed or suspected SARS-CoV-2 infection, must be collected that occur during the screening period and within 100 days following the last dose of nivolumab and for 30 days following the last dose of temozolomide. If applicable, SAEs must be collected that relate to any later protocol-specified procedure (eg, a follow-up skin biopsy). For subjects randomized and never treated with study drug, SAEs should be collected for 30 days from the date of randomization.

The investigator must report any SAE that occurs after these time periods and that is believed to be related to study drug or protocol-specified procedure.

An SAE report must be completed for any event where doubt exists regarding its seriousness.

If the investigator believes that an SAE is not related to study drug, but is potentially related to the conditions of the study (such as withdrawal of previous therapy or a complication of a study procedure), the relationship must be specified in the narrative section of the SAE Report Form.

SAEs, whether related or not related to study drug, and pregnancies must be reported to BMS (or designee) within 24 hours of awareness of the event. SAEs must be recorded on the SAE Report Form; pregnancies on a Pregnancy Surveillance Form (electronic or paper forms). The preferred method for SAE data reporting collection is through the eCRF. The paper SAE/pregnancy surveillance forms are only intended as a back-up option when the eCRF system is not functioning. In this case, the paper forms are to be transmitted via email or confirmed facsimile (fax) transmission to:

**SAE Email Address:** Refer to Contact Information list.

**SAE Facsimile Number:** Refer to Contact Information list.

For studies capturing SAEs through electronic data capture (EDC), electronic submission is the required method for reporting. In the event the electronic system is unavailable for transmission, paper forms must be used and submitted immediately. When paper forms are used, the original paper forms are to remain on site.

**SAE Telephone Contact** (required for SAE and pregnancy reporting): Refer to Contact Information list.

If only limited information is initially available, follow-up reports are required. (Note: Follow-up SAE reports must include the same investigator term(s) initially reported.)

If an ongoing SAE changes in its intensity or relationship to study drug or if new information becomes available, the SAE report must be updated and submitted within 24 hours to BMS (or designee) using the same procedure used for transmitting the initial SAE report.

All SAEs must be followed to resolution or stabilization.

BMS will be reporting adverse events to regulatory authorities and ethics committees according to local applicable laws including European Directive 2001/20/EC and FDA Code of Federal Regulations 21 CFR Parts 312 and 320. A SUSAR (Suspected, Unexpected Serious Adverse Reaction) is a subset of SAEs and will be reported to the appropriate regulatory authorities and investigators following local and global guidelines and requirements.

## **6.2 Nonserious Adverse Events**

A *nonserious adverse event* is an AE not classified as serious.

### **6.2.1 Nonserious Adverse Event Collection and Reporting**

The collection of nonserious AE information (with the exception of non-serious AEs related to SARS-CoV-2 infection) should begin at initiation of study drug. Nonserious AE information should also be collected from the start of a placebo lead-in period or other observational period intended to establish a baseline status for the subjects.

Nonserious AEs should be followed to resolution or stabilization, or reported as SAEs if they become serious (see [Section 6.1.1](#)). Follow-up is also required for nonserious AEs that cause interruption or discontinuation of study drug and for those present at the end of study treatment as appropriate. All identified nonserious AEs must be recorded and described on the nonserious AE page of the CRF (paper or electronic).

All nonserious adverse events (not only those deemed to be treatment-related) should be collected continuously during the treatment period and for a minimum of 100 days following discontinuation of nivolumab treatment, and for 30 days following discontinuation of temozolomide treatment.

Every adverse event must be assessed by the investigator with regard to whether it is considered immune-mediated. For events which are potentially immune-mediated, additional information will be collected on the subject's case report form.

Completion of supplemental CRFs may be requested for AEs and/or laboratory abnormalities that are reported/identified during the course of the study.

### **6.3 Laboratory Test Result Abnormalities**

The following laboratory test result abnormalities should be captured on the nonserious AE CRF page or SAE Report Form (electronic) as appropriate: Paper forms are only intended as a back-up option when the electronic system is not functioning.

- Any laboratory test result that is clinically significant or meets the definition of an SAE
- Any laboratory test result abnormality that required the subject to have study drug discontinued or interrupted
- Any laboratory test result abnormality that required the subject to receive specific corrective therapy.

It is expected that wherever possible, the clinical rather than laboratory term would be used by the reporting investigator (eg, anemia versus low hemoglobin value).

### **6.4 Pregnancy**

If, following initiation of the study drug, it is subsequently discovered that a study subject is pregnant or may have been pregnant at the time of study exposure, including during at least 5 half-lives after product administration, the investigator must immediately notify the Sponsor or designee of this event and complete and forward a Pregnancy Surveillance Form to BMS Designee within 24 hours of awareness of the event and in accordance with SAE reporting procedures described in [Section 6.1.1](#).

In most cases, the study drug will be permanently discontinued in an appropriate manner (eg, dose tapering if necessary for subject safety). Please call Sponsor or designee within 24 hours of awareness of the pregnancy.

The investigator must immediately notify the BMS (or designee) Medical Monitor of this event and complete and forward a Pregnancy Surveillance Form to BMS (or designee) within 24 hours

of awareness of the event and in accordance with SAE reporting procedures described in [Section 6.1.1](#).

Follow-up information regarding the course of the pregnancy, including perinatal and neonatal outcome and, where applicable, offspring information must be reported on the Pregnancy Surveillance Form.

Any pregnancy that occurs in a female partner of a male study participant within 6 months (or as noted in the locally applicable package insert, summary of product characteristics [SmPC] or similar document) of the last dose of TMZ should be reported to Sponsor or designee. In order for BMS to collect any pregnancy surveillance information from the female partner, the female partner must sign an informed consent form for disclosure of this information. Information on this pregnancy will be collected on the Pregnancy Surveillance Form.

## **6.5 Overdose**

An overdose is defined as the accidental or intentional administration of any dose of a product that is considered both excessive and medically important. All occurrences of overdose must be reported as an SAE (see [Section 6.1.1](#) for reporting details).

## **6.6 Potential Drug Induced Liver Injury (DILI)**

Wherever possible, timely confirmation of initial liver-related laboratory abnormalities should occur prior to the reporting of a potential DILI event. All occurrences of potential DILIs, meeting the defined criteria, must be reported as SAEs (see [Section 6.1.1](#) for reporting details).

Potential drug induced liver injury is defined as:

- AT (ALT or AST) elevation > 3 times upper limit of normal (ULN)

AND

- Total bilirubin > 2 times ULN, without initial findings of cholestasis (elevated serum alkaline phosphatase),

AND

- No other immediately apparent possible causes of AT elevation and hyperbilirubinemia, including, but not limited to, viral hepatitis, pre-existing chronic or acute liver disease, or the administration of other drug(s) known to be hepatotoxic.

## **6.7 Other Safety Considerations**

Any significant worsening noted during interim or final physical examinations, electrocardiogram, x-ray filming, any other potential safety assessment required or not required by protocol should also be recorded as a nonserious or serious AE, as appropriate, and reported accordingly.

Immune-mediated adverse events are AEs consistent with an immune-mediated mechanism or immune-mediated component for which non-inflammatory etiologies (eg, infection or tumor progression) have been ruled out. IMAEs can include events with an alternate etiology which were exacerbated by the induction of autoimmunity. Information supporting the assessment will be collected on the subject's case report form.

“Treatment effect,” collected in CNS studies only, is a neurologic AE related to nivolumab attributable to the immune-reaction at or around the tumor site. Most commonly, these are confusion, seizure, weakness, vomiting, aphasia, hydrocephalus, etc (depending on tumor site). Use of “tumor flare” as a single aggregate AE term is preferable to reporting each individual neurologic finding. [Note: MRI findings per se are not AEs.]

## **7 DATA MONITORING COMMITTEE AND OTHER EXTERNAL COMMITTEES**

When required, adjudicated events will be submitted to the DMC and Health Authorities for review on a specified timeframe in accordance with the adjudication documentation.

A Data Monitoring Committee will be established to provide oversight of safety and efficacy evaluation of the entire study and to provide advice to the sponsor regarding actions the committee deems necessary for the continuing protection of subjects. The DMC will be charged with assessing such actions in light of an acceptable benefit/risk profile for nivolumab. The DMC will act in an advisory capacity to BMS and will monitor subject safety and evaluate the available efficacy data for the study. The oncology therapeutic area of BMS has primary responsibility for design and conduct of the study. The DMC will meet at least every 6 months or more frequently as needed on an ad-hoc basis. Information regarding DMC membership, responsibilities, and procedures are detailed in the DMC charter. The DMC will be informed should a safety signal emerge and may convene an ad-hoc meeting on its own initiative. The DMC will review all available data (safety and efficacy) at each meeting. At the conclusion of each DMC meeting the committee, will provide the sponsor with a recommendation to continue, modify or terminate the study protocol based upon their review. Ultimately, decisions regarding the study protocol will be made by the sponsor in conjunction with feedback from investigators and the DMC. Following study unblinding, the DMC will be discontinued, and the sponsor will monitor safety for the subjects remaining on treatment.

## **8 STATISTICAL CONSIDERATIONS**

### **8.1 Sample Size Determination**

This is a Phase 3, randomized, single blinded, multicenter study of RT + TMZ + nivolumab or placebo in adult ( $\geq 18$  years) subjects with newly diagnosed GBM and MGMT-methylated or indeterminate tumors.

The familywise type I error rate for the primary comparisons will be set to 0.05, with 0.01 being allocated to the PFS comparison and 0.04 being allocated to the OS comparison.

The primary objectives of the study are:

- to compare progression-free survival (PFS) in an all-comers group of subjects with newly diagnosed MGMT-methylated or indeterminate GBM subtypes treated with RT plus TMZ combined with nivolumab or placebo.
- to compare overall survival (OS) of subjects with newly diagnosed MGMT methylated or indeterminate GBM subtypes without baseline corticosteroids and regardless of baseline

corticosteroids (ie, all-comers) treated with RT plus TMZ combined with nivolumab or placebo.

These primary objectives on OS will test RT plus TMZ combined with nivolumab or placebo in the following hierarchy via a stratified log rank test:

- 1) OS in newly diagnosed MGMT-methylated or indeterminate GBM subtype without baseline corticosteroids.
- 2) If 1 is significant, OS in newly-diagnosed MGMT-methylated or indeterminate GBM subtype regardless of baseline steroid use (all comers).

The sample size for this study is based on the following assumptions:

- PFS and OS follows exponential distribution
- Median PFS in RT+TMZ arm is 10.0 months
- Hazard ratio (HR) of arm RT + TMZ + nivolumab vs RT + TMZ for PFS is 0.68, translated to median PFS improvement of 4.7 months (10.0 months vs 14.7 months for arm RT + TMZ and arm RT + TMZ + nivolumab, respectively)
- Median OS in RT+TMZ arm is 26.0 months
- Hazard ratio (HR) of arm RT + TMZ + nivolumab vs RT + TMZ is 0.7 for the randomized population with no baseline corticosteroid, translated to median OS improvement of 11.1 months (26.0 months vs 37.1 months for arm RT + TMZ and arm RT + TMZ + nivolumab, respectively)
- Hazard ratio (HR) of arm RT + TMZ + nivolumab vs RT + TMZ is 0.75 for the overall randomized population, translated to median OS improvement of 8.7 months (26.0 months vs 34.7 months for arm RT + TMZ and arm RT + TMZ + nivolumab, respectively)
- Proportion of no baseline corticosteroid population within the entire newly-diagnosed MGMT-methylated or indeterminate GBM subtypes is 0.70

Approximately 693 subjects will be randomized in a 1:1 ratio, stratified by complete or partial resection. Of these 693 subjects, 485 subjects are assumed to be no baseline corticosteroids. Accrual is estimated to take approximately 25 months based on an observed monthly accrual in CA209548 of approximately 28 subjects per month; in the no baseline corticosteroids population, a piecewise accrual of 1, 4, 5, 8, 13, 16, 19, and then 23 subjects per month thereafter is assumed. At least 337 OS events (deaths) in the no baseline corticosteroid population are needed to achieve 88% power using a 2-sided Type 1 error of 4%. This number of events is projected to occur after an additional 44 months of follow-up (ie, at 69 months).

One interim analysis will be conducted on OS in the randomized population with no baseline corticosteroid. It will occur approximately 20 months after accrual is finished or when 70% or 236 OS events is reached which is estimated to occur at 45 months after study start, providing a 58% probability of stopping under H1. The stopping boundaries at the interim and final analyses will

be based on the actual number of OS events at the time of the analysis using Lan-DeMets alpha spending function with O'Brien-Fleming boundaries. If the planned interim analyses occur exactly at the planned number of events, the projected alpha level will be 0.011 and 0.037. See Table 8.1-1. The interim analysis will also be conducted on OS in the overall randomized population. The interim analysis will be conducted at the same time as the interim for the no baseline corticosteroids population in a hierarchy with stopping boundaries at the interim and final analysis based on actual number of OS events at the time of the analysis using Lan-DeMets alpha spending function with O'Brien-Fleming boundaries.

The PFS comparisons will be based on first 558 randomized subjects in all-comers. At least 404 PFS events are needed to achieve 90% power using a 2-sided Type 1 error of 1%. Accrual is estimated to take approximately 23 months and this number of events is projected to occur after an additional 12 months of follow-up (ie, at 35 months).

The technique of alpha-recycling will be used to adjust for multiplicity with details provided in the SAP.

Power calculations were done using East v 6.3 and R.

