**Table 8.1-1: Key Parameters of Sample Size Calculation of PFS and OS**

Primary Endpoint	PFS	OS	OS
Power	90%	88%	87%
Alpha	0.01	0.04	0.04
Hypothesized Median Control vs. exp (months)	10 vs 14.7	26 vs 37.1	26 vs. 34.7
Hypothesized Hazard ratio	0.68	0.7	0.75
Expected number of events for comparison towards primary objective	404	337	494
Accrual Duration (months)	23	25	25
Sample size	558 (all-comers)	485 (no baseline corticosteroids)	693 (all-comers)
Expected number of events at IA	N/A	236	346
FPFV to IA (months)	N/A	45	45
FPFV to LPLV (months)	35	69	69

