7.5.4 Protection of Type I Error

[figure not shown]
The main goals of the study include:

- to compare PFS in the first 558 subjects from all randomized subjects and to prove superiority of radiotherapy+TMZ+nivolumab arm over radiotherapy+TMZ+placebo.
- to compare OS in all randomized subjects without baseline corticosteroids and to prove superiority of radiotherapy+TMZ+nivolumab arm over radiotherapy+TMZ+placebo. OS in all randomized subjects will also be tested for superiority.

PFS will be tested at 1% type I error. OS will be tested at 4% type I error.

To strongly preserve the familywise type I error rate, Bonferroni-based graphical approach by Maurer and Bretz (2013)⁷ will be employed: see Figure 7.5.4-1, for the graphical display of the multiple testing procedure. In this graph defining the test procedure, hypotheses together with their local significance levels are represented by weighted vertices and the propagation rule is represented by weighted directed edges. Algorithm 1 in Maurer and Bretz (2013) provides the rules for updating the local significance levels and the transition weights after rejecting an individual hypothesis. The resulting sequentially rejective testing procedure controls family-wise Type I error rate of 5% in the strong sense, and is uniquely determined by the graph in Figure 7.5.4-1.

Figure 7.5.4-1: Graphical Representation of the Testing Strategy

OS = Overall survival, PFS = Progression-free survival, No BL= all randomized subjects without baseline corticosteroids, AC = all-comers (i.e, all randomized subjects)

[figure not shown]
* first 558 subjects from all randomized population

In Figure 7.5.4-1, each vertex (circle) corresponds to a hypothesis to be tested. The numbers next to the vertices are the initially allocated (endpoint-specific) alpha levels. (Note that it is 0 for OS in all randomized subjects - meaning that they cannot be tested until alpha is passed to them from the OS in all randomized subjects without baseline corticosteroids). The weight (in rectangular frame) associated with a directed edge (line) between any two vertices indicates the fraction of the (local) significance level at the initial vertex that is added to the significance level at the terminal vertex, if the hypothesis at the tail is rejected.

At the time of the PFS analysis, PFS in the first 558 subjects from all randomized population will be tested, at alpha of 0.01.

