The DMC will review the safety and efficacy data from the interim analyses and will recommend if the study should continue with or without changes or should be stopped. More details of the interim analyses are discussed in the Data Monitoring Committee Charter.

The chair of the DMC and the sponsor can call an unscheduled review of the safety data.

Implications of OS Interim Analysis

At the time of the formal interim analysis for superiority of OS, the DMC may recommend continuing or stopping the trial. If the trial continues beyond the interim look, the nominal critical point for the final OS analysis will be determined using the recalculated information fraction at the time of the interim analysis, as described above. The final OS hazard ratio and corresponding confidence interval will be reported whereby the confidence interval will be adjusted accordingly (i.e. using the recalculated nominal α level at the final analysis).

If the trial is stopped for superiority of OS at the interim, all the statistical analyses conducted at the time of interim analysis would be considered final.

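### The 87% power for all-comers OS is stand-alone power at local alpha 0.04; through the testing order the planned chance of rejecting it is about 74% to 85%, depending on boundary, alpha recycling and interim stopping

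*Protocol*

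**What the plan says.** Protocol 8.1 splits the familywise 0.05 two ways, "with 0.01 being allocated to the PFS comparison and 0.04 being allocated to the OS comparison". Within OS it sets an order. The population without baseline corticosteroids is tested first, and the second step reads "If 1 is significant, OS in newly-diagnosed MGMT-methylated or indeterminate GBM subtype regardless of baseline steroid use (all comers". SAP Section 5 repeats this order. SAP 7.5.4 expresses it as a graph of local alpha levels: "Note that it is 0 for OS in all randomized subjects", so this hypothesis has nothing to spend until the no-steroid OS hypothesis is rejected. If PFS is rejected, the same section passes its 0.01 to no-steroid OS, and from there it can reach all-comers OS.

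Protocol Table 8.1-1, headed "Key Parameters of Sample Size Calculation of PFS and OS", shows three columns (PFS, no-steroid OS, all-comers OS) with power 90%, 88% and 87% and the row "Alpha 0.01 0.04 0.04". SAP Table 5-1 prints the same values. Neither table, nor the text around it, says whether 87% allows for the testing order.

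Two further provisions bear on the figure:

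- **Boundary.** For all-comers OS, Protocol 8.1 uses Lan-DeMets O'Brien-Fleming. SAP Sections 5, 7.5.4 and 7.5.5 use Lan-DeMets Pocock.
- **Interim.** SAP 7.5.5 lets all-comers OS be tested at the interim or later once no-steroid OS is significant. It also says "If the trial is stopped for superiority of OS at the interim, all the statistical analyses conducted at the time of interim analysis" are to be treated as final.

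**The concern.** The power row puts 88% and 87% side by side, each against alpha 0.04, as though both tests had that alpha from the start. Only the first does. All-comers OS is rejected only if two correlated tests both succeed, and that probability cannot exceed the stand-alone power of either.

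All-comers OS is part of the primary OS objective and sets the 693-subject, 494-event column. A reader who takes 87% as the chance of success on that part of the objective would be too optimistic. The reader also could not see that the answer depends on which document's boundary applies and on what happens after an interim win.

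**Working it through.** **Inputs** (Protocol 8.1 and Table 8.1-1; SAP Section 5 and Table 5-1). HR "is 0.7 for the randomized population with no baseline corticosteroid" and 0.75 for all-comers. OS events at interim/final: 236/337 without steroids and 346/494 for all-comers, about 70% information in each. Allocation 1:1; OS alpha 0.04, two-sided.

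**Step 1: reproduce the printed figures.** Fixed-sample power is Φ(|ln HR|·√D/2 − z), with z = 2.054 for two-sided 0.04.

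- All-comers: 0.2877 × √494/2 = 3.197; 3.197 − 2.054 = 1.143; power 87.4%.
- No-steroid: 0.3567 × √337/2 = 3.274; 3.274 − 2.054 = 1.220; power 88.9%.

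With two looks and Lan-DeMets O'Brien-Fleming spending:

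| Quantity | Recomputed | Stated |
|---|---|---|
| Nominal levels, interim and final | 0.0109, 0.0367 | 0.011, 0.037 |
| No-steroid crossing at interim | 57.7% | 58% |
| No-steroid power | 88.5% | 88% |
| All-comers power, stand-alone | 86.9% | 87% |

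Every stated OS figure reproduces without the gate, so 87% is stand-alone power.

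**Step 2: correlation (assumption).** The documents give none. The populations are nested, so the all-comers score is the no-steroid score plus an independent score from steroid users. The correlation is √(337/494) = 0.826 at the final look and √(236/346) = 0.826 at the interim. The two planned HRs imply an HR in steroid users of exp[(494·ln 0.75 − 337·ln 0.70)/157] = 0.87.

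**Step 3: apply the gate.** At the final look alone, the bivariate normal probability that both tests reject is 83.4%. For the two-look design, the two score processes were simulated over 2 million trials. Results are percentages:

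| All-comers boundary | OS alpha | Stand-alone | Gated, testing can continue | Gated, every interim no-steroid crossing stops the trial |
|---|---|---|---|---|
| O'Brien-Fleming (Protocol) | 0.04 | 86.9 | 82.9 | 73.5 |
| O'Brien-Fleming (Protocol) | 0.05 | 88.8 | 85.2 | 76.0 |
| Pocock (SAP) | 0.04 | 83.5 | 79.5 to 80.2 | 77.0 to 77.7 |
| Pocock (SAP) | 0.05 | 85.7 | 82.2 to 82.8 | 79.6 to 80.2 |

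The 0.05 rows apply when PFS has been rejected and its 0.01 recycled. The Pocock ranges depend on whether an interim all-comers crossing counts when no-steroid OS is first rejected at the final look; the upper values count it. For O'Brien-Fleming this choice makes no visible difference.

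**Step 4: robustness to the correlation.** For the first row with testing able to continue, any correlation gives a joint probability between 88.5 + 86.9 − 100 = 75.4% and 86.9%.

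**Step 5: size.** Against the printed 87%, the smallest gap is 87 − 85.2 = 1.8 points and the largest 87 − 73.5 = 13.5 points.

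**Step 6: what the stopping column means.** It is an overall probability. In the first row, 57.7% of trials cross on no-steroid OS at the interim, and all-comers OS also crosses there in 81.4% of those: 0.577 × 0.814 = 0.470. The remaining 0.735 − 0.470 = 0.265 comes from trials that reach the final look. With Pocock the 81.4% becomes 93.0%.

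**The case against.** The strongest reply is that 87% is not an error. It is correct for the alpha, HR and event count in its own column, reporting marginal power for a gated hypothesis is common, and the gate is disclosed in the same protocol section. This stands. A reader might infer that the figure was miscalculated, or that the plan promises 87% through the hierarchy; the documents support neither. What is missing is a label and the gated figure.

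A reader might also conclude that the true chance is simply 83%, or 74% with an interim stop. That goes too far, for three reasons.

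- **Recycling.** The SAP 7.5.4 graph passes PFS alpha to OS. PFS has 90% planned power and is planned for month 35, before the OS looks at months 45 and 69. Under the planned alternatives OS would therefore usually be tested at 0.05. Weighting the O'Brien-Fleming rows by 90% and 10%, with PFS taken as independent of OS (an assumption), gives 0.9 × 85.2 + 0.1 × 82.9 = 85.0% and 0.9 × 76.0 + 0.1 × 73.5 = 75.8%.
- **Boundary.** Neither 83% nor 74% fits SAP Table 5-1, because the SAP uses Pocock for all-comers. The 74% pairs the SAP's rule on interim finality with the protocol's boundary.
- **Stopping.** The 74% assumes that every interim crossing ends the trial. SAP 7.5.5 says the DMC may recommend continuing or stopping. Nor is 74% the chance of success given that the trial stopped (Step 6).

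Finally, the practical effect is small. OS is no longer event-driven, conditional power was below 1%, and all-comers OS will be tabulated descriptively (Protocol 8.4.2.1; SAP Section 1, changes to the planned analyses). This also stands.

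**Conclusion.** The point holds as one of labelling and omission. The 87% is marginal power at local alpha 0.04 with O'Brien-Fleming boundaries, and it is not the probability that the design rejects all-comers OS. Every scenario computed under the planned alternatives falls below it, by about 2 to 14 points. In SAP Table 5-1 the 87% does not match that document's own boundary even as stand-alone power, which is 83.5% with Pocock.

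The gated figures rest on the planned HRs of 0.70 and 0.75, the planned event counts, and the correlation implied by nesting. They are sensitive to the HRs: with 0.75 in both steroid groups, which is not the plan's alternative, the O'Brien-Fleming figures at 0.04 would be about 70% and 67%.

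The consequence is limited to the accuracy of the design record. It does not bear on the sample size or on the trial's conclusion.

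**What to change.** 1. Reconcile the all-comers OS boundary between Protocol 8.1 (O'Brien-Fleming) and SAP Sections 5, 7.5.4 and 7.5.5 (Pocock). No single figure can be quoted for both documents until this is done.
2. In each table, label the all-comers figure as marginal power at local alpha 0.04, available only once no-steroid OS has been rejected: 87% for O'Brien-Fleming or 83.5% for Pocock.
3. Beside it, give the power through the hierarchy for the boundary that document uses. O'Brien-Fleming: about 83% (testing can continue) and 74% (every interim no-steroid crossing stops the trial) at OS alpha 0.04, and about 85% and 76% at 0.05 after recycling. Pocock: about 80% and 77 to 78% at 0.04, and about 83% and 80% at 0.05.
4. State the recycling, interim-stopping and correlation assumptions in a footnote.

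The cost is the boundary reconciliation plus a table entry and a footnote in each document. The stated power becomes less favourable. Sample size, alpha allocation and conduct do not change.
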